2.5.3. Vitamin E

Lavine et al. conducted an open-label, pilot study to determine whether supplemental oral vitamin (α-tocopherol) was effective in lowering serum aminotransferases and alkaline phosphatase levels in children with NASH associated with obesity (49). Eleven children younger than 16 years of

age with elevated ALT levels and steatosis by imaging were given oral vitamin E (400-1000 IU/day) for 4-10 months. Daily oral vitamin E administration normalized serum aminotransferase and alkaline phosphatase levels in children with NASH despite no change in the BMI. Mean ALT levels decreased from 175 ± 106 IU/L to 40 ± 26 IU/L (P<0.01) and mean AST levels decreased from 104 ± 61 IU/L to 33 ± 11 IU/L (P<0.002). Interestingly, the levels of transaminases returned to abnormal levels in those individuals who elected to stop therapy with vitamin E. Serum α -tocopherol levels were within normal range at the beginning of the trial and increased significantly with supplementation.

Hasegawa et al. conducted a pilot study evaluating plasma TGF β 1 levels and the efficacy of α -tocopherol in adults with NASH (50). TGF β 1 levels were normal in healthy controls, but were elevated in patients with NASH. After one year of therapy with α -tocopherol, serum aminotransferases and TGF β 1 were significantly reduced. The authors concluded that the long-term therapy with vitamin E was safe and effective in reducing the inflammatory and fibrosis markers in patients with NASH.

In a study of Zucker rats, Soltys et al. demonstrated significantly higher levels of oxidative stress in these animals and that tocopherol therapy significantly improved the levels of oxidative stress and their survival following exposure to lethal levels of ischemia (51).

3.1. **Design overview**

PIVENS is a multi-center, randomized, placebo-controlled, double-masked, double-dummy clinical trial of treatment with pioglitazone, vitamin E, or placebo for patients with NASH. Screening for eligibility and collection of baseline data will span up to 24 weeks. Eligible patients will be randomized to receive either pioglitazone (30 mg q.d.), vitamin E (800 IU q.d.), or placebo for 96 weeks. There will be a 24 week washout period at the end of the treatment phase to assess durability of effects, if any, and to ensure patient safety following the end of treatment. Patients will be asked to participate in the NAFLD Database with annual follow-up visits after the trial has ended. The primary comparisons will be made using an intention-to-treat analysis of the change in NASH activity, as determined from standardized histologic scoring of liver biopsies taken at baseline and at week 96. Secondary outcome measures include change in serum aminotransferase levels, change in anthropometric measurements, change in insulin resistance, change in serum vitamin E levels, and change in health related quality of life scores. A schematic of the trial design is presented below:

PIVENS Trial Design

- · Randomized, multicenter, masked, placebo-controlled study
- Pioglitazone, 30mg qd, and vitamin E, 800 IU qd, compared to placebo

NASH CRN

NASH PIVENS 2\PIVENSProt\Manall_6 4:08 pm Wednesday, April 18, 2007/klc

3.2. Treatment groups

Patients who have signed an informed consent statement and who meet the eligibility criteria will be randomly assigned to one of three groups for 96 weeks of treatment:

Group 1:	Pioglitazone (30 mg q.d.) and vitamin E-placebo (q.d)
Group 2:	Vitamin E (800 IU, natural form, q.d.) and pioglitazone-placebo (q.d.)
Group 3:	Pioglitazone-placebo (q.d.) and vitamin E-placebo (q.d.)

The randomization scheme will assign patients in randomly permuted blocks of assignments stratified by clinical center; block size will be determined randomly. This scheme will ensure that the three groups will be balanced by calendar time of enrollment (to minimize secular effects) and by clinic (to minimize clinic-specific effects of differences in patient populations and management).

The randomization plan will be prepared and administered centrally by the Data Coordinating Center (DCC) but will not require real time interaction with a DCC staff member. Requests for randomizations will be made by the clinics using a web-based application. An assignment will be issued only if the database shows that the patient is eligible, has signed the consent statement, and has had all required baseline data keyed to the database.

3.3. Pioglitazone

Pioglitazone will be administered as a single tablet of 30 mg per day orally with the morning meal. A similar appearing placebo tablet will be taken daily by patients assigned to either the placebo group or the vitamin E group.

The rationale for choosing this dosage hinges on the earlier studies that examined the safety and efficacy of pioglitazone in patients with NASH (46;47). In an open-label, pilot study, Promrat et al. reported that pioglitazone administered in a dose of 30 mg per day is safe and leads to biochemical and histological improvement (47). Similarly, in a prospective study of 21 patients with NASH, Sanyal et al. reported that pioglitazone administered in 30 mg per day in combination with vitamin E led to a significant improvement in hepatic steatosis, ballooning, and Mallory's hyaline compared to vitamin E alone (46).

Pioglitazone, a thiazolidinedione derivative, is an oral antidiabetic agent that primarily works by increasing insulin sensitivity. Studies have shown that pioglitazone improves insulin sensitivity in muscle and adipose tissue and inhibits hepatic gluconeogenesis. It is a highly selective and potent agonist for the peroxisome proliferator-activated receptor-gamma (PPAR γ).

In humans, PPAR γ receptors are found in key target tissues for insulin action such as adipose tissue, skeletal muscle, and liver. Activation of PPAR γ nuclear receptors regulates the transcription of insulin responsive genes involved in the control of glucose production, transport, and utilization. In addition, PPAR γ responsive genes participate in the regulation of fatty acid metabolism.

3.3.1. Rationale for using thiazolidinediones

Points establishing a rationale for the use of thiazolidinediones (TZDs) for treatment of NASH are:

- Insulin resistance is a metabolic hallmark of patients with NASH, and TZDs are effective in improving insulin sensitivity as described above.
- TZDs are effective in the management of several insulin resistance syndromes such as polycystic ovary syndrome (PCOS) (52;53), lipodystrophy associated with HIV (54), and vascular insulin resistance associated with hypertension (55).
- Mouse models of insulin resistance and fatty liver disease have shown that TZDs improve hepatic histology (56).
- Caldwell et al. treated 10 NASH patients with the first clinically available TZD for varying duration up to 6 months and noted improved liver enzymes and decreased necroinflammatory changes in some patients (45).
- In an open label study, Tetri et al. administered 4 mg rosiglitazone twice daily for 48 weeks to 30 patients with biopsy proven NASH. Rosiglitazone was well tolerated and led to improvement in insulin sensitivity, serum ALT levels, hepatic steatosis as demonstrated by CT imaging, and hepatic histology (48).
- In a prospective study of 21 patients with NASH, Sanyal et al. showed that pioglitazone administered for 6 months in combination with vitamin E resulted in a significant improvement in hepatic steatosis, ballooning degeneration, and Mallory's hyaline in comparison to vitamin E alone (46).
- In a recent study by Promrat et al., a 48-week course of pioglitazone (30 mg daily) led to significant improvements in insulin resistance, serum ALT levels, and hepatic histology in 18 patients with NASH (47).
- A recent study by Galli et al. examined the effects of rosiglitazone and pioglitazone on liver fibrosis in rats induced either by toxin administration or bile duct ligation (57). Oral administration of TZDs reduced extracellular matrix deposition and hepatic stellate cell activation in both toxic and cholestatic models of hepatic fibrosis. In vitro, TZD-induced

PPAR γ activation inhibited collagen synthesis induced by TGF- β 1 in human hepatic stellate cells. These data indicate that PPAR γ activation retards fibrosis in vivo and suggests the use of TZDs for the treatment of liver fibrosis.

Collectively, these studies indicate that pioglitazone is likely to result in marked improvement in insulin resistance in patients with NASH and that the change may be associated with substantial improvements in hepatic pathology.

3.3.2. Adverse effects of thiazolidinediones

There are a number of adverse effects that have been attributed to thiazolidinediones (TZDs), which are summarized below:

- **Hepatotoxicity:** The first generation TZD, troglitazone, was associated with idiosyncratic hepatotoxicity and very rare cases of liver failure, liver transplantation, and death. Troglitazone has been withdrawn from clinical use. The second generation TZDs appear to be significantly less hepatotoxic. Second generation TZDs include rosiglitazone and pioglitazone:
 - Rosiglitazone: In pre-approval clinical studies encompassing 3600 patient-years of exposure, there was evidence of drug-induced hepatotoxicity or associated elevations in ALT levels with treatment. In these controlled trials, 0.3% of subjects receiving rosiglitazone had elevations in ALT levels of more than 3 times the upper limit of normal compared to 0.2% on placebo and 0.5% on active comparators. In the postmarketing experience, reports of hepatitis and liver enzyme abnormalities have appeared. Rarely, these reports have included acute liver failure with or without fatal outcome. In the study of rosiglitazone in patients with NASH by Tetri et al. (48), one of 30 subjects was withdrawn from the study due to a sudden 5-fold increase in ALT. Incidentally, this subject had received a short course of prednisone for an unrelated indication.
 - Pioglitazone: In clinical studies worldwide, over 4500 subjects have been treated with pioglitazone, and there was no evidence that it was associated with drug-induced hepatotoxicity or associated elevations in ALT levels. In these trials, the frequency of increase in ALT of more than 3 times the upper limit of normal was 0.26% with pioglitazone and 0.25% with placebo. However, post-marketing reports suggest that pioglitazone usage can lead to increases in the ALT levels, and case-reports have appeared in the literature suggesting that pioglitazone usage can lead to liver dysfunction and jaundice. Pinto et al. from Indiana University reported a case in which pioglitazone use was associated with severe but reversible cholestatic jaundice (peak bilirubin more than 35 mg/dl) (58). In the study of pioglitazone in patients with NASH by Sanyal et al., one of 11 subjects

was withdrawn from the study due to a sudden 6-fold increase in ALT levels (46).

In the study of pioglitazone in patients with NASH reported by Promrat et al., none of 18 patients were withdrawn because of liver test abnormalities (47).

- **Effects on lipids:** Rosiglitazone can lead to an increase in the levels of total cholesterol, LDL, and HDL, and decreases in the levels of free fatty acids. The changes in triglyceride levels during therapy with rosiglitazone are variable. Patients treated with pioglitazone had mean improvements in triglycerides and HDL-cholesterol, but no consistent increases in LDL or total cholesterol (59).
- **Dose dependent weight gain:** When administered at 8 mg per day, rosiglitazone led to a median weight gain of 2.6 kg in clinical studies. In U.S. placebo-controlled monotherapy trials, pioglitazone led to a weight gain ranging between 0.5 to 2.8 kg (59). In the study of Promrat et al., a one-year course of pioglitazone in patients with NASH led to an average weight gain of 3.2 kg, most of which was shown to be due to increase in fat mass (47).
- **Hypoglycemia:** Infrequently, hypoglycemia can occur when TZDs are used as monotherapy for diabetes. When rosiglitazone was used as monotherapy in a dose of 8 mg per day, the incidence of hypoglycemia was 1.6%. The frequency of hypoglycemia was 2% when pioglitazone was used in combination with sulfonylureas (59).
- Edema: TZDs are associated with the development of mild-moderate edema (59). Therefore, caution should be applied while using these agents in subjects with edematous conditions. The edema appears to be due to an increase in the plasma volume.
- **Ovulation:** TZDs may result in ovulation in some anovulatory premenopausal women (59). Thus, subjects taking TZD agents are at an increased risk of becoming pregnant. Therefore, adequate contraception is necessary in premenopausal women.
- **Hemoglobin/hematocrit:** The use of TZDs leads to a consistent but mild drop in hemoglobin and hematocrit (mean drop in hemoglobin less than 1 g/dL) (59). This is thought to be dilutional in nature as a result of increase in the plasma volume.
- **Risk of drug interactions:** Pioglitazone is metabolized by multiple cytochrome P450 isoforms such as CYP2C8 and CYP3A, and there are some data which suggest that pioglitazone may induce CYP3A. This leads to a theoretical possibility that co-administration of a CYP3A inhibitor (such as diltiazem, macrolides, imidazoles, etc) may lead to disturbed in vivo disposition of pioglitazone. However, this is not believed to be a significant concern as pioglitazone will be metabolized by CYP2C8 in situations when CYP3A is inactive.

Strategies for protecting patients against the possible adverse effects of pioglitazone are discussed in section 5.8.1.1.

3.4. Vitamin E

The formulation of vitamin E to be used in this study is the natural form of vitamin E (RRR- α -tocopherol, formerly known as *d*- α -tocopherol) at a daily dosage of 800 IU administered orally via a single softgel. A similar appearing placebo softgel will be taken daily by patients assigned to either the pioglitazone group or the placebo group.

The rationale for the use of vitamin E for treatment for NASH was developed in section 2.5.3. Double-masked trials and large population studies have shown that oral vitamin E at 800 IU daily dose is safe with no significant side effects (60;61). The vitamin E dose chosen for this trial (800 IU q.d.) is within the range of vitamin E dosage that has been tested for the treatment of human NASH in previous pilot studies (46;49;62;63). For example, in a pilot study, Kugelmas et al. tested the effect of step I American Heart Association diet plus exercise with or without 800 IU of vitamin E daily (63).

Although the use of antioxidants may improve insulin resistance and thereby may reduce the incidence of new-onset diabetes, it is reasonable to assume that the magnitude of risk of new-onset diabetes in patients randomized to the vitamin E group is the same as placebo (i.e., 18 patients during the 96 weeks of treatment). Measures to identify patients who develop diabetes during the trial and their management strategy are described in section 5.8.1.2.

3.5. Rationale for placebo treatment group

Currently, there is no proven pharmacotherapy available for the treatment of NASH. In the current study, we intend to test the hypothesis that therapeutic agents to modify insulin resistance (pioglitazone) or oxidative stress (vitamin E) improve liver histology in patients with NASH. The efficacy of each of these agents will be compared to placebo. As there is no proven pharmacologic therapy for NASH, using a placebo for comparative purposes is justified. In this study, subjects will take pioglitazone-placebo and vitamin-E placebo.

3.6. Standard treatment recommendations

In addition to the study medication, patients will receive a standardized set of recommendations about life-style modification (dietary modification, weight loss, exercise), use of prescription or non-prescription medicines or herbal remedies or dietary supplements, consumption of alcohol, and management of various co-morbid illnesses. These recommendations have been prepared by the NASH CRN Standards of Care Committee and are approved by the NASH CRN Steering Committee. This will help ensure that the patients in all groups receive standard of care treatment for NASH.

4. Patient selection

4.1. Recruitment

Approximately 240 patients will be recruited from the eight clinical centers of the NASH CRN (averaging 30 patients per center) over a two-year period:

- Case Western Reserve University, Cleveland, OH (PI: [name]),
- Indiana University, Indianapolis, IN (PI: [name]),
- Duke University, Durham, NC (PI: [name] [name]),
- Saint Louis University, St Louis, MO (PI: [name]),
- University of California, San Diego, CA (PI: [name]),
- University of California, San Francisco, CA (PI: [name]),
- University of Washington, Seattle, WA (PI: [name]),
- Virginia Commonwealth University, Richmond, VA (PI: [name]).

Eligible patients will be identified and recruited at the participating clinical centers subject to the inclusion and exclusion criteria listed later in this chapter. Clinics will be required to recruit sufficient overall numbers of minorities and women so that results can be generalized to these populations.

Each clinic will develop a recruitment plan. These plans will vary from clinic to clinic depending on the available pools of patients and local recruitment resources.

4.2. Inclusion criteria

In order to qualify for inclusion in the trial, patients must satisfy the following inclusion criteria:

Based on a liver biopsy obtained no more than 6 months prior to randomization (patient must not have used antiNASH medications in the 3 months prior to the biopsy), histological evidence of NASH as defined by a NASH activity score, which is EITHER (1) a composite score of 5 or greater (where each component score for steatosis, hepatocyte ballooning, and lobular inflammation is 1 or more) as judged by the local NASH CRN pathologist with a finding of possible (defined as suspicious/borderline/indeterminate) or definite steatohepatitis as judged by the local NASH CRN pathologist, OR (2) a composite score of 4 (where each component score for steatosis, hepatocyte ballooning, and lobular inflammation is 1 or more) as judged by the local NASH CRN pathologist and a finding of definite steatohepatitis as judged by the local NASH CRN pathologist and a finding of definite steatohepatitis as judged by the local NASH CRN pathologist and a finding of definite steatohepatitis as judged by the local NASH CRN pathologist and a finding of definite steatohepatitis as judged by the local NASH CRN pathologist and a finding of definite steatohepatitis as judged by the local NASH CRN pathologist and two additional NASH CRN pathologists (i.e., at least two of the three pathologists must find definite steatohepatitis).

17

2. Patient must be 18 years of age or older as of the initial screening interview.

4.3. Exclusion criteria

Patients who satisfy any of the following exclusion criteria will be ineligible for enrollment in the trial:

- 1. Current or history of significant alcohol consumption for a period of more than 3 consecutive months within 5 years prior to screening (significant alcohol consumption is defined as more than 20 g/day in females and more than 30 g/day in males, on average) or inability to reliably quantify alcohol consumption
- 2. Clinical or histological evidence of cirrhosis as judged by study physician (clinical cirrhosis is defined by presence of any of the following: albumin less than 3 g/dL, INR greater than 1.3, conjugated bilirubin greater than 2 mg/dL, varices, or ascites)
- 3. Evidence of other forms of chronic liver disease:
 - Hepatitis B as defined by presence of hepatitis B surface antigen (HBsAg)
 - Hepatitis C as defined by presence of hepatitis C virus (HCV) RNA or positive hepatitis C antibody (anti-HCV)
 - Evidence of ongoing autoimmune liver disease as defined by the presence of anti-nuclear antibody (ANA) of greater than 1:80 and consistent liver histology; or history of autoimmune hepatitis as judged by study physician
 - Primary biliary cirrhosis as defined by elevation of alkaline phosphatase greater than upper limit of normal and anti-mitochondrial antibody (AMA) of greater than 1:80 and consistent liver histology
 - Known primary sclerosing cholangitis and suggestive liver histology
 - Wilson's disease as defined by ceruloplasmin below the limits of normal and consistent liver histology
 - Alpha-1-antitrypsin deficiency as defined by a suggestive liver histology (confirmed by alpha-1 antitrypsin level less than normal at the discretion of the study physician)
 - History of hemochromatosis or iron overload as defined by presence of 3+ or 4+ stainable iron on liver biopsy
 - Drug-induced liver disease as defined on the basis of typical exposure and history
 - Known bile duct obstruction
 - Suspected or proven liver cancer
 - Any other type of liver disease other than NASH
- 4. Serum alanine aminotransferase (ALT) greater than 300 U/L
- 5. Fasting plasma glucose of 126 mg/dL or greater at initial screening or at the oral glucose tolerance test done at the second screening visit
- 6. Serum creatinine of 2.0 mg/dL or greater

- 7. Use of drugs historically associated with NAFLD (amiodarone, methotrexate, systemic glucocorticoids, tetracyclines, tamoxifen, estrogens at doses greater than those used for hormone replacement, anabolic steroids, valproic acid, or other known hepatotoxins) for more than 2 consecutive weeks in the 2 years prior to screening
- 8. Use of antidiabetic drugs (insulin, biguanides, glucosidase inhibitors, sulfonylureas, meglitinides, metformin, thiazolidinediones) in the 3 months prior to liver biopsy or the 3 months prior to randomization
- 9. Use of antiNASH drugs (thiazolidinediones,vitamin E, metformin, UDCA, SAM-e, betaine, milk thistle, gemfibrozil, anti-TNF therapies, probiotics) in the 3 months prior to liver biopsy or the 3 months prior to randomization
- 10. Use of a non-stable dose of statins (atorvastatin, fluvastatin, lovastatin, pravastatin, rosuvastatin, simvastatin) or fibrates (clofibrate, fenofibrate) in the 3 months prior to biopsy or the 3 months prior to randomization
- 11. Known intolerance to thiazolidinediones or vitamin E
- 12. Vitamin E supplementation of greater than 100 IU/day
- 13. Inability to safely obtain a liver biopsy
- 14. History of diabetes mellitus
- 15. History of total parenteral nutrition in the year prior to screening
- 16. History of bariatric surgery (jejunoileal bypass or gastric weight loss surgery) or currently undergoing evaluation for bariatric surgery
- 17. History of biliary diversion
- 18. Known positivity for antibody to Human Immunodeficiency Virus
- 19. Known heart failure of New York Heart Association class 2, 3, or 4
- 20. Active, serious medical disease with likely life-expectancy less than 5 years
- 21. Active substance abuse, such as alcohol or inhaled or injection drugs, in the year prior to screening
- 22. Women of childbearing potential: positive pregnancy test during screening or at randomization or unwillingness to use an effective form of birth control during the trial
- 23. Women: Breast feeding
- 24. Any other condition which, in the opinion of the investigator would impede compliance or hinder completion of the study
- 25. Failure to give informed consent

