Screening visit 2: Patients will provide blood for banking (measurements to be done on banked serum will include vitamin E level). Patients will complete a nutritional questionnaire (Block 98), a health-related quality of life questionnaire (SF-36), life time drinking history questionnaire (Skinner), functional activity questionnaire, and liver symptoms questionnaire. Laboratory tests include: GGT, prothrombin time, HbA1c, hepatic panel (total and direct bilirubin, AST, ALT, alkaline phosphatase), microalbuminuria. A standard 75 g OGTT with fasting serum glucose, insulin, and C-peptide will be administered. Women of childbearing potential must have a negative pregnancy test. Patients will undergo a DEXA scan to estimate total body fat. All patients will be given information on a healthy life style and diet appropriate for their weight and other factors.

The NASH CRN clinic data system will include software to check patient eligibility based on keyed data forms. The eligibility check task may be run at any time, and there is no limit on the number of times it may be run. The output from the task will list the eligibility checks that the patient has failed and a summary finding that the patient is eligible or ineligible for the trial. Thus staff can use this task to identify the items that still need to be completed, keyed, or verified after data from screening visit 1 are keyed and again after data from screening visit 2 are keyed. The randomization visit should not take place until the eligibility check indicates that the patient is eligible except for the items that can be completed only at the randomization visit.

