5.4. Follow-up visits

Patients will return for follow-up visits at 2, 4, 8, 12, 16, 24, 32, 40, 48, 56, 64, 72, 80, 88, 96, and 120 weeks after randomization. Thus, starting at 16 weeks after randomization, patients will be seen at 8 week (2 month) intervals through 96 weeks. Each visit will have an interval of time surrounding the ideal date for the visit during which the visit may be done and the data included in the trial database. The ideal date for a visit is the exact anniversary from randomization. Visit windows will be constructed to be contiguous, so that at any point in time, some visit window is open, subject to a check on the minimum separation required between consecutive visits. The specific procedures to be completed at each of the follow-up visits are:

- Week 2 visit: Blood draw for hepatic panel (total and direct bilirubin, AST, ALT, alkaline phosphatase); pregnancy test (for women of child-bearing potential).
- Week 4 visit: Follow-up medical history including review of medications, adverse effects, and interim drinking history; focused physical examination, including height, weight, waist, hip measurements, vital signs (temperature, heart rate, respiratory rate, blood pressure), and liver signs; blood draw for hepatic panel (total and direct bilirubin, AST, ALT, alkaline

phosphatase); pregnancy test (for women of child-bearing potential). Dispense study drug and review study drug adherence with patient.

- Week 8 visit: Follow-up medical history including review of medications, adverse effects, and interim drinking history; focused physical examination, including height, weight, waist, hip measurements, vital signs (temperature, heart rate, respiratory rate, blood pressure), and liver signs; blood draw for hepatic panel (total and direct bilirubin, AST, ALT, alkaline phosphatase); pregnancy test (for women of child-bearing potential). Dispense study drug and review study drug adherence with patient.
- Week 12 visit: Blood draw for hepatic panel (total and direct bilirubin, AST, ALT, alkaline phosphatase); pregnancy test (for women of child-bearing potential). Review study drug adherence with patient.

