5.8.1.1. Safety issues related to thiazolidinediones

• Hepatotoxicity: The first generation TZD, troglitazone, was associated with idiosyncratic hepatotoxicity, and very rare cases of liver failure, liver transplantation, and death. Troglitazone has been withdrawn from clinical use. The second-generation thiazolidinediones appear to be significantly less hepatotoxic. A review of risk of hepatotoxicity associated with second-generation TZD agents is provided in section 2.4. We intend to minimize the risk of hepatotoxicity (or its consequences) (a) by closely monitoring the aminotransferase levels during the study period (at 2, 4, 8, 12, 16, 24, 32, 40, 48, 56, 64, 72, 80, 88, 96, and 120 weeks after randomization), (b) by discontinuing study medication in patients with severe hepatotoxicity (defined as ALT or AST greater than 10 times the ULN in the local lab OR absolute AST or ALT greater than 500 U/L OR serum total bilirubin at least 2.5 mg/dL and at least half of it is direct bilirubin), (c) by avoiding the other potential hepatotoxic agents, and (d) by instructing the patients about self-identification of symptoms associated with hepatotoxicity (i.e., yellow eyes, dark urine, unexplained anorexia, asthenia, or right upper quadrant abdominal pain).

Those who exhibit ALT or AST elevation that is not to the extent described above but who develop a 1.5-fold or greater elevation in ALT or AST from their baseline value and

absolute ALT or AST greater than 250 U/L OR total bilirubin at least 1.5 mg/dL and at least half of it is direct bilirubin OR develop symptoms suggestive of acute hepatotoxicity (i.e., jaundice, nausea, vomiting, abdominal pain, fatigue, anorexia, dark urine) will have their liver biochemistries checked on a weekly basis. If ALT, AST, and/or bilirubin levels decline or stabilize, subjects will have their liver biochemistries checked monthly for 3 months and then according to the protocol schedule. If ALT or bilirubin continues to rise on two consecutive measurements following the initial rise in ALT, AST or bilirubin or if the patient develops symptoms of hepatotoxicity, subjects will be considered to have developed significant hepatotoxicity and the study medication will be discontinued indefinitely.

Patients in whom the study medication has been discontinued due to significant hepatotoxicity will be followed according to the protocol and will be offered a liver biopsy at the conclusion of the study.

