5.13. Procedures for unmasking treatment assignment

Treatment assignments are double masked throughout the study until all data collection for the PIVENS trial has been completed (i.e., after completion of the 24 week post trial Follow-up for all patients). Every effort will be made to maintain the masking throughout the study except in emergency situations. The code of specific pharmacological treatment will not be broken without the knowledge of the clinical center's principal investigator.

Unmasking of study medication will occur under the following conditions:

- Severe allergic reaction (Stevens-Johnson Syndrome): Study medication is stopped indefinitely. The patient, primary care provider (PCP), and the investigator will be unmasked.
- **Pregnancy during the study**: Study medication will be stopped indefinitely, and the coded medication will be unmasked. The patient, PCP, and investigator will be notified of the assigned treatment and the associated risks of teratogenicity.
- **Development of hepatotoxicity**: Study medication will be discontinued according to the guidelines in section 5.8.1.1. The patient, PCP, and the investigator will be unmasked.
- **New onset diabetes**: The patient will be referred to their PCP and managed according to the stepped care approach defined in section 5.8.1.2. The patient and PCP may be unmasked to the study medication but the investigator will continue to be masked.

In unforeseen situations where the clinical center principal investigator considers unmasking is in the best interest of the participant's health and well being, unmasking may be done after notifying the Executive Committee.

The Data and Safety Monitoring Board will review all instances of unmasking that occur.

6. Statistical design and analysis

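### A patient who meets the entry criteria can already satisfy the severe-hepatotoxicity stopping definition before the first dose, through bilirubin or AST

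*Protocol*

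**What the plan says.** **Entry (Protocol 4.3).** Item 2 excludes cirrhosis and gives the markers of clinical cirrhosis as "albumin less than 3 g/dL, INR greater than 1.3, conjugated bilirubin greater than 2 mg/dL, varices, or ascites". This is the only bilirubin limit among the exclusions. Item 4 excludes "Serum alanine aminotransferase (ALT) greater than 300 U/L". No item names AST or total bilirubin, although both are in the hepatic panel drawn at screening visit 2 (5.2).

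**Stopping (Protocol 5.8.1.1).** Severe hepatotoxicity leads to discontinuation of study medication. It is defined as "ALT or AST greater than 10 times the ULN in the local lab OR absolute AST or ALT greater than 500 U/L", or as "serum total bilirubin at least 2.5 mg/dL and at least half of it is direct bilirubin". None of these limbs refers to the patient's own starting value. The lower tier, which leads to weekly testing, does have such a term for the enzymes: it applies to those who "develop a 1.5-fold or greater elevation in ALT or AST from their baseline value", together with an absolute condition.

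**Consequence (Protocol 5.13).** Under the entry on the development of hepatotoxicity: "Study medication will be discontinued according to the guidelines in section 5.8.1.1. The patient, PCP, and the investigator will be unmasked".

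**Timing (Protocol 5.4 and Appendix 9.3).** The first scheduled hepatic panel after randomization is at week 2. None is scheduled at the randomization visit.

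**The concern.** An on-treatment safety rule is meant to detect harm that arises under treatment. If the entry criteria admit patients who already satisfy it, the rule can fire with no change in the patient.

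Three things are at stake for each such patient:

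- **Treatment.** Medication would stop after about 2 of 96 planned weeks (2/96, or about 2%). A patient with a week 96 biopsy would still be analysed in the assigned group.
- **Masking.** Patient, primary care provider and investigator would all learn the assignment, in a trial that otherwise keeps the code closed until all data are collected.
- **Attribution.** A pre-existing abnormality could be handled as drug hepatotoxicity, in a trial where liver safety of a thiazolidinedione is a named concern.

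The abnormality precedes randomization, so it is expected equally in all three arms, placebo included. The effect is therefore loss of treatment and masking and noise in the safety data, not a systematic bias toward one arm.

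**Working it through.** The check compares the set of values that passes entry with the set that meets the stopping definition. The protocol gives no figure of its own to reproduce here.

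**Bilirubin (no assumption needed).** Let T be total and D direct (conjugated) bilirubin in mg/dL.

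- Entry (4.3, item 2): D ≤ 2.0, with T unrestricted.
- Stopping (5.8.1.1): T ≥ 2.5 and D ≥ T/2.
- Both together: D ≥ 2.5/2 = 1.25, and T/2 ≤ 2.0, so T ≤ 4.0.

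| T | D that is eligible and meets the stopping definition |
|---|---|
| 2.4 | none (T is below 2.5) |
| 2.5 | 1.25 to 2.0 |
| 3.0 | 1.5 to 2.0 |
| 3.5 | 1.75 to 2.0 |
| 4.0 | 2.0 only |
| 4.1 | none (would need D ≥ 2.05) |

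Example: T = 3.0 and D = 1.8. Entry is passed because 1.8 ≤ 2.0. The stopping definition is met because 3.0 ≥ 2.5 and 1.8/3.0 = 60%, which is at least half.

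**AST.** The stopping limit is AST above the smaller of 10 × ULN and 500 U/L, where ULN is the local upper limit of normal. There is no entry limit. Any AST above the stopping limit is therefore formally eligible. This is an absent limit, not an overlap of two limits.

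**ALT (depends on an assumption).** Entry requires ALT ≤ 300 U/L, so the 500 U/L limb cannot be met at that value. The 10 × ULN limb can be met only if 10 × ULN < 300, that is, ULN < 30 U/L. The protocol gives no ULN. For assumed values:

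| Assumed local ULN (U/L) | Eligible ALT that meets the stopping definition (U/L) |
|---|---|
| 20 | above 200, up to 300 |
| 25 | above 250, up to 300 |
| 29 | above 290, up to 300 |
| 30 or more | none |

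**Sequence.** A patient in the bilirubin region at screening visit 2 fails no exclusion that states a bilirubin value. If the values are the same at week 2, the definition in 5.8.1.1 is met as written, and 5.13 attaches unmasking to discontinuation under that section.

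**The case against.** The strongest reply is that judgement would catch these patients before randomization. Section 4.3 leaves cirrhosis to the study physician. It excludes bile duct obstruction, drug-induced liver disease and any liver disease other than NASH, and it has a general exclusion for conditions that would hinder completion. Under 5.3, an assignment is generated only if clinic staff indicate that they want to randomize. An affected patient must also have no cirrhosis, albumin of at least 3 g/dL and INR no higher than 1.3. This stands as a reason to expect few cases. It does not reconcile the texts, because none of these provisions is tied to the stopping limits.

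A second reply is that 5.13 speaks of hepatotoxicity developing, which suggests a new event. That is a fair reading of intent. But 5.13 defers to 5.8.1.1, whose severe definition requires no change from baseline, so the sections pull in different directions.

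The two rules also serve different purposes, one screening for cirrhosis and the other monitoring treatment, and each can be applied as written. The problem is the result for a small group of patients, not that the rules cannot be applied.

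Three stronger readings go beyond the documents:

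- **The weekly-testing tier as a further route to stopping.** Its bilirubin trigger also has no baseline term, but it leads only to more frequent testing. Discontinuation then needs a continued rise on two consecutive measurements, or symptoms. An unchanged, asymptomatic patient is neither stopped nor unmasked.
- **An established ALT overlap.** It is conditional on a local ULN below 30 U/L, which the protocol does not state.
- **Certain entry into the DSMB's hepatotoxicity reports.** Section 6.6 refers to incident hepatotoxicities. Whether a stable pre-existing value would be counted as incident is an inference.

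**Conclusion.** The point holds for bilirubin and AST. For bilirubin it follows from the two written limits alone: direct 1.25 to 2.0 mg/dL with total 2.5 to 4.0 mg/dL, at least half of it direct, is both eligible and within the severe-hepatotoxicity definition. For AST it follows from the absence of any entry limit. For ALT it is only a possibility.

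That such a patient would be stopped and unmasked rests on two assumptions: the value is still there at week 2, and 5.8.1.1 is applied literally.

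The number affected cannot be derived, because the documents give no distribution of bilirubin or AST in the target population. It is likely to be small. One such patient is 1 of 80 in an arm, or 1.25%, so the primary comparison is not threatened. The point is still worth correcting because each case costs treatment and masking and blurs the liver-safety signal.

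**What to change.** Reconcile sections 4.3, 5.8.1.1 and 5.13 so that a stable pre-treatment bilirubin or AST value cannot by itself trigger discontinuation and unmasking as drug hepatotoxicity. Which passage changes, and how, is for the clinical team. No threshold or new exclusion is proposed here, and none is needed at the weekly-testing level. In the same edit, the sites' local ALT ULN values should be checked to see whether any is below 30 U/L.

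Then compare the hepatic panel from screening visit 2 with the reconciled rule before randomization. The electronic eligibility check described in 5.2 and 5.3 is a natural place for this.

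The cost is wording in up to three sections and one check on values already collected. The downside is that a few patients may be handled differently.
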